10.5 SAFETY ANALYSIS

All safety analyses will be performed on the safety analysis population based on all available data by the three study groups separately.

10.5.1 ADVERSE EVENT

AE will be classified as pretreatment, intraoperative, or postoperative. The number and the percent of eyes reporting at least 1 AE of a given type will be summarized.

Additionally, the number of reports of each type of AE will be provided.

Each AE will be summarized by incidence, percentage and the corresponding 95% confidence interval.

10.5.2 BEST CORRECTED VISUAL ACUITY (BCVA)

The number and percent of eyes reporting with BCVA of 20/20 or better, 20/25 or better, 20/32 or better, 20/40 or better, worse than 20/40 to 20/80, worse than 20/80 to 20/200, and worse than 20/200 at each visit will be summarized. The number and percent of eyes reporting BCVA of increase \geq 10 letters, increase 10 letters, increase \geq 5 letters to < 10 letters, within 5 letters change, decrease \geq 5 letters to < 10 letters, decrease 10 letters, and decrease \geq 10 letters at each postoperative visit will be calculated.

10.5.3 OTHER SAFETY OUTCOMES

The number and percent of eyes reported with each kind of slit lamp findings, gonioscopy findings, and dilated fundus examination findings at each visit will be provided.

The descriptive statistics for the continuous variables will be derived for the visual field mean deviation (MD) and pattern standard deviation (PSD).

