8.10 MANAGEMENT OF IOP AFTER SURGERY

In general, the primary consideration for the reintroduction of hypotensive medication is the preservation of the retinal nerve fiber layer, optic nerve and visual field.

[REDACTED] Administration of glaucoma medication in subjects with IOP < 21 mmHg will be considered on a case-by-case basis by the study Investigator and the sponsor.

No more than one ocular hypotensive agent should be added at a single visit or within a 2-week period, without prior approval of the sponsor.

In the event of a steroid response increase in IOP due to prolonged anti-inflammatory regimen, the guidelines above to treat increase in IOP should be followed; however, topical hypotensive medications should be discontinued once the topical steroid has been discontinued.

Since the study population is undergoing angle surgery involving use of an ophthalmic viscoelastic agent, which is known to cause IOP spikes in some patients in the immediate postoperative period, use of glaucoma medications in the first month after surgery will be allowed at the discretion of the study Investigator. This short-term use of glaucoma medications in the immediate postoperative period will not be considered "rescue therapy" and will not be considered in the effectiveness analyses for the study.

For subject safety, a change in medical therapy may be implemented or additional surgical measures may be performed at any time during the study at the Investigator's discretion in the event it is required. The primary concern of the Investigator and

Sponsor at all times is the health and safety of the subjects. Usage of hypotensive medications specifically indicated for prevention of IOP spikes following Nd:YAG capsulotomy and administered for up to 72 hours after Nd:YAG capsulotomy will not be considered rescue therapy.

Medications which have been re-started by the Investigator may be discontinued if the Investigator's judgment is that the target intraocular pressure has been reached and the continued use of some or all of the therapy may not be required. Discontinuation of medications after re-introduction is recommended to be in the reverse order of re-introduction. The rationale for discontinuation should also be documented in the subject's medical record.

A record of all ocular hypotensive medications added, discontinued or changed will be documented on the appropriate CRF for each scheduled visit or on a CRF for an Unscheduled Visit, if necessary.

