8.12 SUBJECTS LOST TO FOLLOW-UP

Subjects who do not show up for a follow-up must be contacted to attempt to have them come for the follow-up. For those subjects who cannot be reached, every attempt to contact with the subject should be documented. If a subject misses two consecutive follow-up visits without any contact with the study staff, the subject will be considered lost-to-follow-up unless there is a further communication by the subject.

9 ADVERSE EVENTS (AEs)

Adverse Events are defined below. Adverse events that occur in the eye during the trial, whether they are considered to be device related or not, must be documented in the subject's records. Date of the event, its severity, treatment (if any) and the assessed relationship of the event to the study device will be recorded on the Adverse Event Form. Conditions which exist at the time the subject is enrolled will be considered pre-existing conditions and do not need to be recorded as adverse events unless they increase in severity during the study. Sites should document any known existing medical and ophthalmic conditions at the time of screening.

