10.4 EFFECTIVENESS ENDPOINTS AND ANALYSIS METHODS

Descriptive statistics on continuous variables will include mean, standard deviation, median, minimum, and maximum. Confidence intervals for change from baseline will be included for selected endpoints. Categorical variables will be summarized using frequency counts and percentages. Exact confidence intervals for point estimates may be provided. Statistical testing will be one-sided with a significance level of 0.025 or two-sided significance level of 0.05 unless specify otherwise. Data listings of individual subject data may be provided.

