19.5 VISUAL FIELD EXAMINATION

Visual fields must be automated threshold visual fields, 24-2 Humphrey Stimulus III. The SITA Standard must be used for the visual field conducted at the pre-operative evaluation and all subsequent evaluations. Visual fields should be reliable as determined by the Investigator. A visual field done within 6 months prior to the subject informed consent date and in accordance with the 24-2 SITA Standard requirements can be used for the baseline evaluation. For visual fields that do not meet the reliability standards, the test should be repeated within two weeks.

Visual fields are to be performed with a non-dilated pupil unless, in the opinion of the investigator, the pupil is so miotic that dilation is required (e.g., < 3mm). If dilation was performed at screening, it should be performed at all subsequent visual field examinations. However, dilation should not be performed before the IOP measurement on the appropriate visits.

It is recommended that the following set up occur for the visual field:

SITA Standard 24-2 test

- using the white, size III stimulus,
- Foveal Threshold ON,
- Head Tracking ON and
- Vertex Monitoring OFF.

The appropriate trial lens as defined by the perimeter should be used.

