19.6 DILATED FUNDUS EXAMINATION

A mydriatic should be used to dilate the pupil so that an examination of the fundus can be conducted with an indirect ophthalmoscope and slit lamp biomicroscopy (with contact lens, Hruby lens or 60-, 66-, 78-, or 90 diopter lens). The appearance of the optic disc, macula, vessels and periphery should be evaluated and reported on the Baseline form. A measurement of the cup to disc ratio should be made and reported.

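### Visual field MD and PSD get only group descriptive statistics in 10.5.3; adding within-eye change and a per-eye count of worsening would give a more sensitive safety measure.

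*Combined protocol and SAP*

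**What the plan says.** Section 10.5.3 gives visual fields one sentence: "The descriptive statistics for the continuous variables will be derived for the visual field mean deviation (MD) and pattern standard deviation (PSD". Section 10.4, written for the effectiveness variables, explains the term: "Descriptive statistics on continuous variables will include mean, standard deviation, median, minimum, and maximum". Section 10.5.3 mentions no change from baseline, no amount of worsening and no number of eyes.

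Other safety data are handled per eye. Section 10.5.2 counts eyes by letters of BCVA gained or lost at each postoperative visit. Section 10.5.3 counts eyes with slit lamp findings, "gonioscopy findings, and dilated fundus examination findings at each visit will be provided". Section 10.5.1 says of adverse events: "The number and the percent of eyes reporting at least 1 AE of a given type will be summarized". Under section 9, pre-existing conditions "do not need to be recorded as adverse events unless they increase in severity during the study".

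The field test is standardised in section 19.5: "The SITA Standard must be used for the visual field conducted at the pre-operative evaluation and all subsequent evaluations". Section 8.10 says that the main consideration in restarting medication "is the preservation of the retinal nerve fiber layer, optic nerve and visual field". Section 19.6 says of the disc: "A measurement of the cup to disc ratio should be made and reported". No analysis section names the cup-to-disc ratio.

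**The concern.** Standardising the field test makes repeat fields comparable within an eye, but the stated analysis makes no use of that pairing. Two features of the design make visit-level summaries of MD hard to read as a measure of harm.

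- **Cataract.** A visually significant cataract is an inclusion criterion (7.1), and it is removed at surgery. The preoperative and postoperative fields are taken through different media, so MD may shift for reasons unrelated to the optic nerve. The documents do not quantify that shift.
- **Withdrawal.** Under 8.10, a subject who needs another glaucoma procedure is followed for a limited time and then withdrawn. Those eyes leave the later visit summaries, and they are not a random subset.

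If a small share of eyes lost a clinically relevant amount of field, an arm's mean MD could look stable. Such loss is irreversible (section 3), and the trial plans 36 months of follow-up.

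**Working it through.** **Arm size.** The synopsis gives 411 completers at 12 months, allocation 1:1:1 and about 10% dropout. Per arm: 411/3 = 137. Inflated: 137/0.90 = 152.2, rounded up to 153, and 3 × 153 = 459, which reproduces the plan's total. The SD and effect size behind 411 are redacted and are not needed here.

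**Assumptions not in the documents.** Between-eye SD of MD: 3-4 dB. SD of within-eye change: 1.5-2 dB. Extra eyes worsening in one arm: 10% (or 5%), each by 5 dB. Stable eyes falsely flagged by retest noise: 2%, 5% or 10%. A true 5 dB loss is always flagged. Section 10.5 plans no between-arm safety tests, so power serves only as a yardstick of sensitivity (two-sided 0.05, normal approximation).

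**Within one arm.** 14 of 137 eyes losing 5 dB move the mean by 14 × 5/137 = 0.51 dB. The 95% half-width of the arm mean is 1.96 × SD/√137 = 0.50 dB (SD 3) or 0.67 dB (SD 4). With 7 eyes the shift is 0.26 dB, inside both. A count would show 14/137 = 10.2% (exact 95% CI 5.7% to 16.6%) or 7/137 = 5.1% (2.1% to 10.2%).

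**Mean MD levels, two arms.** Shift = 0.10 × 5 = 0.5 dB. SE = SD × √(2/137) = 0.36 (SD 3) or 0.48 (SD 4). Power = Φ(0.5/SE − 1.96) = 28% or 18%.

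**Mean within-eye change.** The affected arm is a mixture, so its variance is SD² + 0.10 × 0.90 × 5² = SD² + 2.25. SE = √[(2·SD² + 2.25)/137].
- SD 1.5: √(6.75/137) = 0.222; power 61%.
- SD 2: √(10.25/137) = 0.274; power 45%.

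The same mixture variance would lower the figures for levels slightly, to 17-26%.

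**Counts.** With false-flag rate q, the affected arm is flagged at q + 0.10 × (1 − q). SE is unpooled.

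| q | Affected arm | Power |
|---|---|---|
| 2% | 11.8% | 90% (91% if rounded to 12%) |
| 5% | 14.5% | 77% |
| 10% | 19.0% | 57% |

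**Extra 5% of eyes.** Levels: 7-10%. Change (mixture variance SD² + 0.05 × 0.95 × 25): 16-23%. Counts: about 52% (2% vs 7%), 33% (q = 5%) and 21% (q = 10%).

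So part of the gain comes from moving from levels to within-eye change. The rest comes from counting, and depends on how noisy the flag is.

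**The case against.** The strongest objection is that worsening may already be counted. Section 10.5.1 reports the number and percent of eyes for each event type, with 95% confidence intervals. Glaucoma is pre-existing in every eye, so section 9 makes an increase in its severity an adverse event, and 9.1 makes sight-threatening events serious. The list in 9.2 covers events associated with glaucoma and is obscured. Its surviving footnotes contain numerical criteria, so a field or disc criterion may be there too. This stands: a reader might infer that no number of worsened eyes will be reported, and the documents do not support that.

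A reader might also infer that field loss is averaged away entirely. If the 10.4 list applies, the minimum and maximum are shown, and 10.4 allows listings of individual data. But a minimum MD is one eye, mixes baseline severity with loss, and gives no rate.

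Nor do the documents say that cup-to-disc ratio is reduced to a count of findings. Section 10.5.3 does not name it, and 19.6 mentions only the baseline form for fundus findings. The visit schedule (Table 1) is not legible, so the timing of fields, and whether the ratio is measured after surgery, cannot be checked.

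Finally, comparing 18-28% with 91% would flatter counts: it sets levels at a wide SD against a flag with little noise. Against change scores and a noisier flag, the gain is smaller. Visual field is also not among the safety endpoints in 6.2.

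**Conclusion.** The point holds as a reporting gap in the safety analysis. Section 10.5.3 states neither within-eye change nor a per-eye count of worsening for MD or PSD, and visit-level summaries suit this design poorly. A possible adverse event entry does not replace a prespecified analysis of the measured MD, because the legible text gives no field threshold for an increase in severity.

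Under the assumptions above, the 10% scenario runs from about 18-28% (levels) to 45-61% (change) and 57-91% (counts). With q at 10% and a change SD of 1.5 dB, the count does no better than mean change, which is a reason to report both. All SDs, loss sizes and flag rates are assumed, and 137 per arm applies at 12 months; later visits may have fewer eyes. The primary analysis and sample size are unaffected.

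**What to change.** In 10.5.3 keep the descriptive statistics and add, for the safety population by arm and visit:

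1. Within-eye change in MD and PSD with 95% confidence intervals, from the preoperative field and, separately, from the first reliable postoperative field. The second reference avoids the change in media but misses any loss before it, so both are needed.
2. Number and percent of eyes, with exact 95% confidence intervals, whose MD worsened by at least a prespecified reporting amount. Align that amount with any field criterion in the adverse event list. Add a version confirmed on a later scheduled field, where the schedule has one.
3. Eyes withdrawn after a secondary IOP procedure, shown at their last available field, since they would otherwise drop out of the later counts as well.
4. Change in cup-to-disc ratio, only if it is measured postoperatively.

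If the adverse event list already defines field worsening, a cross-reference can supply the definition for item 2; the other items still apply.

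The cost is a short addition to the analysis text and two or three tables. If the schedule includes postoperative fields, no new test or visit is needed. The downside is some retest noise in single-field counts, which the confirmed version limits. The reporting amount describes data and is not a rule for managing patients.

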10.6 INTERIM ANALYSIS

An interim analysis providing descriptive statistics for the outcomes may be completed following completion of the Month 6 follow-up visit by 80% of the randomized subjects. Endpoints listed below will be analyzed at an interim analysis. No device effectiveness will be claimed based on the interim analysis outcomes.

Effectiveness outcomes up to 6 months will be summarized descriptively:

1. Percent of eyes with a $\geq 20\%$ reduction in IOP with no increase in IOP-lowering medications compared to screening visit
2. Percent of eyes with IOP between 6 and 18 mmHg with no increase in IOP-lowering medications compared to screening visit
3. Percent of eyes with IOP between 6 and 21 mmHg with no increase in IOP-lowering medications compared to screening visit
4. Reduction in mean IOP from screening visit; and
5. Reduction in mean number of IOP-lowering medications from screening visit for the subjects who are on medications at the screening visit

Safety endpoints:

1. Rates of ocular adverse events (intraoperative, postoperative)
2. Reduction in best corrected visual acuity (BCVA) from baseline (note: reduction in BCVA due to PCO will not be treated as a safety event)

10.7 DEVIATION FROM THE STATISTICAL PLAN

Any deviations from the statistical plan will be noted in the final report.

11 MONITORING PROCEDURES

Sight Sciences or contract research organization (CRO) personnel will monitor the study in a manner consistent with FDA regulations, good clinical practices and the clinical research standards adopted by Sight Sciences. Study monitoring will be executed using on-site and remote monitoring visits. Study monitoring will involve the following elements:

- Site Qualification: Sight Sciences or CRO personnel will meet with investigators and clinical study staff prior to the initiation of the study in order to review the adequacy of the subject population, facilities, and equipment with respect to the needs of the study, and to familiarize the investigator with the study protocol. If Sight Sciences or the CRO have recently been involved with an investigator for another study, a site qualification visit may not be necessary.

- Site Initiation: Sight Sciences and/or CRO personnel will meet with the investigator(s) and clinical study staff when the site is ready to begin enrolling subjects in order to train them in how to properly select subjects, perform the study procedure, and record study data. This visit will include, but not be limited to a review of the following:
 - Detailed review of the protocol
 - Informed consent procedures
 - Instructions for the surgical procedure
 - Records and reports
- Interim Monitoring: Sight Sciences or CRO personnel will conduct routine visits during the course of the study to review charts, perform source document verification, ensure proper adherence to the study protocol, and to review regulatory documents. Interim monitoring visits and telephone consultation will occur as necessary during the course of the study to ensure the proper progress and documentation of the study findings.
- Study Close Out Visit: At the conclusion of the trial there will be a study closure visit during which several actions, including but not limited to the following, will be performed:
 - A final inspection of the study binder
 - Accountability and return of all devices and non-consumable ancillary study supplies to the sponsor
 - Discussion of record retention requirements with the investigator
 - Close-out notification to the IRB

12 DATA AND QUALITY MANAGEMENT

12.1 DATABASE MANAGEMENT

The study database will be designed using an electric data capture (EDC) system that is compliant with 21 CFR Part 11 and relevant guidance documents. The EDC will be developed and maintained by an independent, qualified data management firm.

The database will incorporate time-stamped audit trails, protection of human subjects, restricted access, and data security at the component level. Each database module, including each individual eCRF, will be validated by conducting a series of standard tests that demonstrate usability and correctness of the database system. The database will be maintained on an ongoing basis and will be routinely backed up.

12.2 SUBJECT IDENTIFICATION

The subjects will be identified by a six-digit subject number composed of a double-digit study identification number, a two-digit center identification number followed by a three-digit sequential subject number. A subject identification number will be assigned

after informed consent is obtained. This will ensure that identifiable subject information has been removed and kept confidential.

12.3 SUBJECT ACCOUNTABILITY

All subjects enrolled and treated in this clinical investigation shall be monitored for the duration of the investigation. The clinical investigation shall be considered completed when all subjects that have been enrolled in the investigation have reached the final reporting period, excluding subjects who were withdrawn.

12.4 CONFIDENTIALITY

All medical records associated with the clinical investigation will be made available for review by Sight Sciences personnel, its contract research organization (CRO) and governmental/regulatory agencies involved. The results of the study may be published in the future for scientific and marketing purposes, but the identity of each subject will not be revealed. All records will be stored in a secure area at the investigator's facility, the CRO, the data management firm and at Sight Sciences, Inc.

12.5 SOURCE DATA AND CASE REPORT FORMS

Source data will be entered into a validated electronic system at each site by trained personnel in accordance with 21 CFR Part 11 requirements. Electronic entries will be verified against corresponding source data at the sites and queried/corrected if needed to the extent possible. Medical site records serve as source data. In addition, data that are collected exclusively for the purpose of this study and not normally recorded in the subjects' medical records can be collected directly on any study CRFs or tools provided by the sponsor, and these will serve as the source data.

Source data and study CRFs are to be maintained at the site in the subject records or in the medical records. All data entries must be made in accordance with ALCOA (Attributable, Legible, Contemporaneous, Original, Accurate) standards and GDP (Good Documentation Practices).

Study data acquired from sites will be collected on Electronic Case Report Forms (eCRFs) for submission to sponsor. Sites will enter data entered on source documents into the electronic case report forms for Sponsor review and analysis.

12.6 RETENTION PERIOD

Clinical sites are to retain any and all clinical trial material (documentation, photographs, etc.) for a period of two years from the date a marketing application is approved or two years after the investigation has been discontinued, or as directed by their institutional document retention requirements, whichever is the longest. After that time, the items must be returned to Sight Sciences for archiving.

13 PROTOCOL MODIFICATIONS AND DEVIATIONS

Protocol modifications may occur during the study. Each will be approved by the sponsor before implementation. Each will undergo Institutional Review Board (IRB) review and approval, as necessary.

Any deviations from this protocol intended to protect the life or physical well-being of a subject in an emergency are to be reported to Sight Sciences, Inc. as well as the IRB as soon as possible, and no later than 5 working days after the emergency occurred.

All protocol deviations will be documented using the Protocol Deviation CRF or Source Tool.

14 DEVICE FAILURES AND MALFUNCTIONS

All study device failures (OMNI surgical system) or malfunctions should be recorded on the Customer Experience Form and reported to Sight Sciences Customer Service [contact]).

